- iv. **Binocularity testing.** The examiner will determine if strabismus is present using a unilateral cover tests as well as Hirschberg evaluation. Subjects with an existing strabismus are not eligible. Subjects who develop a strabismus during the study period will be referred for further evaluation and retained for follow up.
- v. **Accommodative response and lag** will be measured with the Schaeffel PowerRefactor and by dynamic retinoscopy with no refractive correction worn.

The Schaeffel PowerRefactor is an infrared, binocular photorefractometer capable of measuring the meridional refractive error, and therefore the dynamic accommodative response, of both eyes simultaneously at 25 Hz. Photorefraction in general and this instrument specifically have been shown to compare well to conventional retinoscopic measures of accommodation with the added advantage of measuring accommodative response and its variability in both eyes over a more extended period of time (Blade and Candy, 2006; Braddick, Atkinson, French, et al., 1979; Howland, Dobson and Sayles, 1987; Rosenfield, Portello, Blustein, et al., 1996; Seidemann and Schaeffel, 2003). The PI's experience with this instrument is that maintaining attention is critical to the validity of measurements. Inattention and the drifting of gaze from central fixation on the accommodative target interfered with the comparability of measurements to conventional dynamic retinoscopy (Gabriel and Mutti, 2009). To filter out readings that might be obtained when fixation is poor, the "Gaze Control" setting on the PowerRefactor will be set to 15° in "Binocular" refraction mode.

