There is no universally accepted outcome measure for infant accommodative response, therefore the analysis in this phase will be somewhat exploratory. The simplest metric to calculate would be the average accommodative response. However, variability in that response provides a useful perspective that distinguishes the infant with stable accommodation from the one that is less well-controlled or exhibits more of a searching accommodative behavior. Variability will be added as a covariate in analyses of the accommodative response. The simple standard deviation in accommodation is one measure of this variability. Another approach would be to look for periodic variability through Fourier analysis of the response. This analysis would be exploratory. Analyses are typically of 10 second segments of response. If infants are too unsteady to give such lengths of uninterrupted data, then the analysis may not be feasible. If the analysis can be done, then power at low, mid, and high temporal frequencies will be used as covariates in the analyses of accommodative response. Other potential metrics might be lag-minutes or diopter-minutes, essentially area-under-the-curve summary measures of diopters of lag, or alternatively, diopters of accommodative response per minute of recording.

- vi. **Cycloplegic refractive error** will be measured at all visits. Refractive error will be measured by **cycloplegic retinoscopy** by a masked examiner (primary outcome of the treatment phase of the study). The parents of the subject will be instructed not to discuss the treatment group the patient is in to the masked examiner. Measurements will occur 30 minutes after drop instillation. One drop of proparacaine 0.5% will be instilled in each eye, followed by two drops of cycloplegic agents. The drops used for cycloplegia are the following:
 - 1. Tropicamide (1%) will be used only at the screening visit
 - 2. Cyclopentolate (1%) will be used during all remaining visitsThe neutral point for the horizontal meridian is recorded first, then the neutral point for the vertical meridian. If the axes are oblique, the true meridian is measured by projecting the retinoscopy beam on to a protractor on the wall. **SureSight autorefraction** will be also be performed on both eyes from 35cm by the investigator (unmasked).

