- vii. **Peripheral refractive error.** Peripheral refractive error will be assessed by the examiner using the SureSight autorefractor as an estimate of the ocular shape during emmetropization. The subject's gaze is directed towards toys or interesting targets. Measurements will be made at 30° in both left and right gaze (a total of 2 peripheral gazes). This will be measured at the baseline, 9 month, and 18 month visit.
- viii. **Parental refractive error status.** The parent(s) refractive error will be obtained as in the Berkeley Infant Biometry Study (BIBS), from the prescription for glasses provided by the eye care provider for parents who wear refractive correction. If the parents report not having had a recent eye

examination, refractive error status will be estimated with the autorefractor without cycloplegia.

ix. Survey. Additional data will be collected via a survey administered at the baseline visit and will request information regarding:

1. Parental age at the infant's birth
2. Parental smoking status
3. Alcohol consumption
4. Infant birthweight
5. Birth order
6. Minor complications of pregnancy and delivery
7. Years of education completed for each parent
8. Family income
9. Ethnic identification for each parent and for the child (assigned by the parent)

x. Additional data. The following data will be obtained at each visit:

1. Significant infant illness
2. Medications given to the infant
3. Nutritional history
4. Compliance with spectacle wear. Parents will fill out a form at each follow up visit listing how compliant the subject was wearing spectacles. Parents of the subjects will be able to classify compliance as very good ($\geq 75\%$ of the time), good ($\geq 50\%$ of the time but less than 75% of the time), fair ($\geq 25\%$ of the time but less than 50% of the time), or poor ($\leq 25\%$ of the time). Parents will be given a pre-printed calendar to help them keep track of compliance on a daily basis. This will be turned into the investigator at the next follow up.

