5. Compliance with visual engagement and vision therapy exercises. Parents will out a form at each follow up visit listing how compliant they were with performing accommodative therapy with the subject. Parents of the subjects will list how many minutes they were able to engage in the recommended visual activity each day. Parents will be given a pre-printed calendar to help them keep track of compliance on a daily basis. This will be turned in to the investigator at the next follow up.

xi. Ocular health. The ocular health will be assessed at the baseline examination and at the final visit with a direct ophthalmoscope, transilluminator with a 20 Diopter condensing lens, or binocular indirect ophthalmoscope.

d. Measurement and Visit Schedule

Measurement	S	V1/B	V2	V3	V4	V5	V6	V7
Target Age (months)	2	3	4.5	6	9	12	15	18
Cycloplegic refractive error w/ SureSight	X		X	X	X	X	X	X
Cycloplegic refractive error w/ Retinoscopy	X	X	M	M	M	M	M	M
Peripheral Refractive error w/ Sure Sight		X			X			X
Accommodative response and lag w/ Power Refractor		X	X	X	X	X	X	X

Accommodative response and lag w/ MEM		X	X	X	X	X	X	X
Ocular Health		X						X
Ocular Motility		X	X	X	X	X	X	X
Ocular Alignment		X	X	X	X	X	X	X

LEGEND: S = Screening visit at Pediatrician's office

V1/B = Baseline Examination

V2 = Visit 2, 4.5 months of age

V4 = Visit 4, 9 months of age

V6 = Visit 6, 15 months of age

M = Performed by an examiner

V3 = Visit 3, 6 months of age

V5 = Visit 5, 12 months of age

V7 = Visit 7, 18 months of age

M = Performed by an examiner masked to the infant's group assignment

e. **Visit Schedule.** The target and acceptable dates for each study visit are given below. If a monthly examination cannot be completed within the acceptable range, that visit will be considered as missed. It will be important to stress to parents at enrollment the importance of attending each of these scheduled visits. The acceptable range for the 6 and 18 month examinations has been extended to 14 days after the target date to maximize the probability that this examination can be completed.

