f. **Development of Strabismus.** The subject population of this study is at risk for developing strabismus (Anker et al., 2004; Cotter, 2007; Pascual et al., 2014). This will be discussed with the parents of potential subjects during screenings and during the consent process prior to the baseline examination. If a subject develops a strabismus, the subject will be discontinued from treatment in the study. The subject cannot remain in either arm of the study because of the different standard of care in prescribing philosophy that occurs with the development of strabismus (typically providing a full refractive correction for hyperopia). The subject will remain in the study and will continue to be followed for observation of all study measurements and outcomes. The subject's parents will have the option of their child remaining under the care of [name] in the Ohio State University College of Optometry Pediatric clinic, or any other doctor within the Ohio State University College of Optometry, or seek or be referred to another provider for a second opinion or for patient care. Any visits or treatment of strabismus or any clinical sequelae of the strabismus would be at the discretion of the licensed eye care provider and separate from the study. Follow up visits related to the study will follow the same schedule and contain the same measurements listed in the protocol.

E. **Internal Validity.** There are no threats to internal validity. All procedures performed in the examination are standard procedures that have been performed frequently in other studies. Threats to external validity might be present in selection bias. The sample of patients to be recruited will be identified at Riverside Pediatrics Associates by screenings of age appropriate infants. The screenings will be performed by [name], [name], or a nurse that has been adequately trained. The age, gender, and ethnicity of these patients might not be a true representation of the general population of full term, healthy infants.

F. **Data Analysis.** All data analysis will be performed using SPSS (Version 24). Statistical significance will be assessed using two-sided tests with an alpha level of 0.05. Data from both eyes will be included in all analyses and techniques to control for intra-subject correlations will be used.

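### The plan says it has no threats to internal validity, but its schedule masks only cycloplegic retinoscopy, leaving the between-arm comparison of peripheral refraction not planned as masked

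*Combined protocol and SAP*

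**What the plan says.** Section E asserts "There are no threats to internal validity" and gives one reason: "All procedures performed in the examination are standard procedures that have been performed frequently in other studies". It does not mention masking.

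Masking is dealt with elsewhere:

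- **Retinoscopy.** D.c.vi has cycloplegic retinoscopy done "by a masked examiner (primary outcome of the treatment phase of the study", and parents are told not to reveal the group to that examiner. In the D.d schedule this row carries M at V2 to V7. The legend reads "M = Performed by an examiner masked to the infant's group assignment".
- **Central SureSight.** D.c.vi says it is "performed on both eyes from 35cm by the investigator (unmasked". The row is coded X at screening and at V2 to V7, and is blank at V1.
- **Peripheral SureSight.** D.c.vii says "Peripheral refractive error will be assessed by the examiner using the SureSight autorefractor as an estimate of the ocular shape during emmetropization". No masking status is given. The row is coded X at V1, V4 and V7.
- **Accommodation.** D.c.v says response and lag "will be measured with the Schaeffel PowerRefactor and by dynamic retinoscopy with no refractive correction worn", and names no examiner. The PowerRefractor row and the row "Accommodative response and lag w/ MEM" are coded X throughout V1 to V7.

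Section F compares the change in relative peripheral refraction between arms at 9 and 18 months, by t-test and by ANCOVA. For accommodation it specifies no between-arm test. It relates effort and lag to change in refractive error.

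**The concern.** That a procedure is standard says nothing about whether the person performing it knows the allocation. The plan accepts this for its primary outcome, where it brings in a masked examiner, so the absolute statement in section E does not match the plan's own precautions.

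Allocation is easy to learn here. One arm wears spectacles and the other does not, and under D.e the investigator edges and dispenses the lenses and telephones the parents.

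The eye-shape prediction in section I rests on relative peripheral refraction, and that outcome is tested directly between arms. The readings are instrument-based, but at 30° in an infant they depend on directing the child's gaze to a target. An operator who knows the group and expects a particular shape change could influence the comparison without intending to. With about 13 infants per arm, a modest systematic shift is not negligible.

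MEM depends on an examiner's judgement and is also not planned as masked. It is the lesser concern: the PowerRefractor measures the same construct objectively, and D.c.v describes the accommodation analysis as somewhat exploratory.

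**Working it through.** **1. The masking statements side by side**

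| Measure | Follow-up code (D.d) | Masking in the text | Use in section F |
|---|---|---|---|
| Cycloplegic retinoscopy | M, V2 to V7 | Masked | Primary: between-arm change at 9 and 18 months |
| Central SureSight | X, V2 to V7 | Explicitly unmasked | Possible central term in relative peripheral refraction; source not stated |
| Peripheral SureSight | X, V4 and V7 | None stated | Between-arm change at 9 and 18 months |
| PowerRefractor | X, V2 to V7 | None stated | Related to change in refractive error |
| MEM | X, V2 to V7 | None stated | Related to change in refractive error |

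Only one row is masked. For central SureSight the lack of masking is explicit. For the last three rows it follows from X as against M and from silence in the text, so not planned as masked is as far as the documents go.

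**2. Illustration of size, for the peripheral refraction t-test only**

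The plan gives no figure to reproduce here. Inputs from the documents: two-sided alpha 0.05 (section F) and 13 evaluable infants per arm (sample-size paragraph before section C). Assumptions: no true effect; a systematic shift of 0.25D in one arm; SD of change 0.75, 1.0 or 1.5D; one value per infant. The plan gives no SD for change in relative peripheral refraction. The 1.5D value borrows its SD for change in central refraction.

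Standard error = SD × √(2/13). Noncentrality = 0.25 / standard error. Degrees of freedom = 2 × 13 − 2 = 24, critical value 2.064. The false-positive rate is the probability that a noncentral t falls beyond ±2.064.

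| Assumed SD | Standard error | Noncentrality | False-positive rate |
|---|---|---|---|
| 0.75D | 0.294 | 0.850 | 12.9% |
| 1.0D | 0.392 | 0.637 | 9.4% |
| 1.5D | 0.588 | 0.425 | 6.9% |

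With no shift the rate is 5%.

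**3. Would an operator shift cancel?**

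Relative peripheral refraction is peripheral minus central. If both came from the same instrument and operator, a shift common to both would drop out. Section F does not say which central measure is used, and no central SureSight is scheduled at V1. A baseline difference taken wholly from SureSight is therefore not available from the schedule, and cancellation cannot be relied on.

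**The case against.** The strongest reply is that the plan masks what matters most. The primary outcome is masked at every follow-up visit, and leaving instrument-based secondary measures to the investigator is a recognisable use of limited staff. That stands, and it keeps this a minor point.

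A reader might go further in four ways that the documents do not support:

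- **That the main refractive comparison is compromised.** It is not. Follow-up retinoscopy is masked.
- **That all the accommodation evidence is observer-judged.** The PowerRefractor is an infrared instrument recording at 25 Hz, with a gaze limit and rule-based removal of artefacts. Attention still matters, as D.c.v says, but the reading is not an examiner's judgement.
- **That the inflated error rates apply to the accommodation analysis.** Section F plans no between-arm test of lag, so a two-sample calculation does not describe it.
- **That the plan declares every one of these measures unmasked.** It does so only for central SureSight.

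It is also fair to object that nothing in the documents supports a 0.25D operator effect, and that the choice of SD drives the result. Both are correct, so the figures show sensitivity and do not estimate actual bias.

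Finally, masking everything could do harm. Bringing the masked examiner in before the drops to take MEM could expose that person to the spectacles or the allocation, and would supply a reading that could inform the primary retinoscopy. This stands, and it limits the fix.

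**Conclusion.** The sentence in section E is not consistent with the plan's own masking schedule and should not remain. The practical weakness is narrow: the between-arm analyses of change in relative peripheral refraction at 9 and 18 months rest on readings that are not planned as masked. MEM is a secondary concern. Under the assumed 0.25D shift, the false-positive rate of the peripheral t-test would rise from 5% to somewhere between 6.9% and 12.9%. That range depends on the assumed shift and SD, neither of which the documents supply for this outcome. The point is a low-cost improvement and not a flaw in the primary analysis.

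**What to change.** 1. At V4 and V7, have the examiner who already performs masked retinoscopy take central and peripheral SureSight immediately after recording retinoscopy. The primary reading is then already recorded and cannot be affected. Change those cells in D.d from X to M, and bring D.c.vi and D.c.vii into line.
2. Replace the sentence in section E with a list of the measures that stay unmasked. These include central SureSight at the other follow-up visits and any accommodation measure that is not masked.
3. Mask MEM and PowerRefractor only if this can be done without showing the masked examiner the glasses or the allocation before the primary retinoscopy. Otherwise label them unmasked and limit the mechanism claims accordingly.

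The cost of the first step is a few more minutes of the masked examiner's time at two visits. That examiner is already scheduled at both, though the documents do not state how much time is available. The second step is a text edit, and so is the labelling option in the third.

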The proposed protocol for this study differs from other early intervention studies. The current proposal will provide a greater amount of under-correction and will occur at a younger age. Results from a longitudinal study performed by the primary investigator of this study suggest that 1.00D of under-correction in a three-month old infant would result in a very small change between 3 and 9 months of age (Figure 1) (Mutti et al., 2005). Previous studies have used only 1.00 to 2.00D of under-correction in early intervention (Atkinson et al., 2000; Ingram et al., 2000). Based on the information provided in Figure 1, the range of effective emmetropization occurs between +1.00D and +4.00D of hyperopia. More aggressive under-correction (greater than 1.00D to 2.00D) would be needed in higher hyperopes to ensure that they reach the range of effective emmetropization between +1.00D and +4.00D. The effective range of emmetropization is addressed in more detail in Figure 2. If the emmetropization endpoint is defined as reaching a refractive error of $\leq +2.00$ D by 18 months of age, then 80% or more of early refractive errors of +4.00D or less at 3 months of age will resolve by 18 months of age using no intervention. For early refractive error between +5.00D to +7.00D, which is what is proposed in this study, the percentage that reach the emmetropization endpoint of $\leq +2.00$ D drops to between 50% and as low as 20%. The range of refractive errors outside of +5.00D and +7.00D appears to be outside of the effective range of emmetropization.

Previous studies initiated early correction treatment in the latter half of the first year of life (Atkinson et al., 2000; Ingram et al., 2000). The majority of the emmetropization process occurs before 9 months of age (Mutti et al., 2005). As children get older, hyperopia becomes less effective in promoting refractive changes. Hyperopic infants between 3 and 9 months of age show a decrease of hyperopia by an average of 0.81D while infants between 9 and 18 months show a decrease of only 0.23D (Mutti et al., 2009). Perhaps previous studies did not find a treatment effect because they initiated treatment too

[figure not shown]

Figure 1. The change in hyperopia between 3 and 9 months as a function of hyperopia at 3 months.

[figure not shown]

Figure 2. The probability of emmetropization at 18 months ($\leq +2.00$ D) as a function of refractive error at 3 months.

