Sample size calculations were performed using the formula adapted by Lindsey to take advantage of the power gained from obtaining repeated measurements across time and eyes (Lindsey, 2001). Data from the Berkeley Infant Biometry Study (BIBS) were used to obtain an estimate of the within-subject/within-visit repeatability of refractive error and the correlation of these measurements across time. The standard deviation for change in refractive error from 3 to 9 months of age from infants with hyperopia $>+5.00\text{D}$ enrolled in BIBS was 1.17D. Data from Atkinson et al. suggests a standard deviation of 1.50D and Ingram et al. give a standard deviation for change is assumed to be 1.36D (Atkinson et al., 2000; Ingram et al., 2000). To provide the most conservative estimate of sample size, the standard deviation of change is assumed to be 1.50D. If a new, difficult, expensive treatment strategy is to be adopted, the benefit must be substantial. The ordinary decrease in hyperopia in uncorrected, highly hyperopic infants might be 1.2D to 1.34D (Atkinson et al., 2000; Ingram et al., 2000). We would expect that there would be little enthusiasm for this new approach if the decrease in hyperopia in treated infants was not on the order of 3.00D (an improvement compared to controls of 1.75D). Using these parameters, a sample size of 13 in each randomized group will be needed ($\alpha=0.05$, $\beta=0.1$, two-sided test). If we estimate that 10% of the infants may not complete the follow up, 30 infants need to be enrolled with 15 randomly assigned to each of the two randomized groups. The rather large difference relative to its standard deviation to be detected ($1.75/1.50 = 1.17$) along with the increase in power obtained by taking repeated refractive error measurements help to keep the sample size low. However, given the prevalence of high hyperopia (more than $+5.00\text{D}$) in the population of 3 months old infants, a sample size of 30 eligible infants (for randomization, not including the case series) is not trivial. Up to 10 eligible infants will be enrolled in the case series portion of the study. One of the major efforts in this project will be screening the 900 infants needed to find those that are eligible.

C. Measurement/Instrumentation

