The basic analysis will be a two-sample t-test comparison of the change in refractive error between the two groups at 9 months and again at 18 months of age. Analysis of Covariance (ANCOVA) will be used to compare the change in refractive error between the two treatment groups adjusting for any possible confounding variables. Refractive error at 3 months along with any other identified confounders will be included as covariates in the analysis. Randomization of infants into the two treatment groups should protect against confounding, however, testing will be performed and adjustments made for imbalances in confounders between groups.

The relationship of accommodative effort and accommodative lag with change in refractive error between 3 and 9, or 3 and 18 months will be analyzed by repeated measures analysis of variance. We will fit a linear functions describing the relationship between change in refractive error and accommodation as the repeated factor, either effort or lag. A significant effect for type of accommodation will indicate that the greater slope is the better explanation of the driving force for change in refractive error.

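### Section F tests the same treatment contrast by an unadjusted t-test and by an ANCOVA with an open covariate list, and does not say which result decides

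*Combined protocol and SAP*

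**What the plan says.** All references are to the combined protocol and SAP.

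- Section F, Data Analysis, names the first test: "The basic analysis will be a two-sample t-test comparison of the change in refractive error between the two groups at 9 months", repeated at 18 months.
- The next sentence adds a second test of the same contrast: "Analysis of Covariance (ANCOVA) will be used to compare the change in refractive error between the two treatment groups". Its covariates are 3-month refractive error plus other confounders not listed in advance. The paragraph ends by promising tests for imbalance between groups, and adjustment where imbalance is found.
- One significance level covers everything: "Statistical significance will be assessed using two-sided tests with an alpha level of 0.05". The same paragraph requires both eyes in all analyses, with an unnamed method for the within-infant correlation.
- Section D.c.vi makes masked cycloplegic retinoscopy the primary outcome. It names neither a deciding test nor a deciding age.
- Section D.b.i (Randomization) describes a 15/15 random list with no stratification on refraction.
- The last paragraph of section F repeats the t-test and ANCOVA pair for relative peripheral refraction.
- The sample size paragraph does not mention covariate adjustment.

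**The concern.** Two tests of one hypothesis, each at the full 0.05, give two p-values and two estimates. If they fall on opposite sides of 0.05, the trial has no agreed result, and reporting whichever is favourable raises the type I error above its stated level. The ANCOVA is not one fixed model either. Its covariate list depends on imbalance tests run on the trial data, so the t-test competes with a set of possible models. If the t-test is taken as the headline, any chance difference between arms in 3-month refraction stays in the estimate, since nothing in the allocation or the test accounts for it. With about 26 completers, one or two infants can decide such a disagreement.

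**Working it through.** **The plan's own figure.** The sample size paragraph says "a sample size of 13 in each randomized group will be needed ($\alpha=0.05$, $\beta=0.1$, two-sided test", with "an improvement compared to controls of 1.75D" as the difference and "the standard deviation of change is assumed to be 1.50D". The simple formula gives n = 2(1.960 + 1.282)² × (1.50/1.75)² = 15.44, so 16 per group (17 with an exact t-test). The plan cites a repeated-measures formula without giving its correlation. Multiplying 15.44 by (1 + ρ)/2 for two eyes gives 13 when ρ is about 0.56 to 0.68 (at ρ = 0.6, 12.35, rounded up to 13). So 13 is compatible with the named method but cannot be verified. The loss step reproduces: 13/0.9 = 14.4, so 15 per arm and 30 in total.

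**Baseline-change correlation r (not given in the documents).** For +5.00D to +7.00D, section II says "the percentage that reach the emmetropization endpoint of" +2.00D or less drops to between 50% and 20%. Read this as 50% at +5.00D and 20% at +7.00D, with final refraction normal with SD s.
- Mean decrease is 3.00D at +5.00D and 5 − 0.842s at +7.00D.
- Slope of decrease on baseline = (2 − 0.842s)/2. This is 0.51 at s = 1.17D, 0.43 at 1.36D and 0.37 at 1.50D, the three SDs of change in the sample size paragraph.
- Assumed baseline SD: 0.50D to 0.58D (an even spread over 2D gives 2/√12 = 0.58).
- r = slope × baseline SD / s, from 0.369 × 0.50/1.50 = 0.12 to 0.508 × 0.577/1.17 = 0.25. Baseline then explains about 1.5% to 6% of the variance of change.

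**Either-test error.** Simulation with 13 per arm, one value per infant, no effect, each test at 0.05, 2,000,000 trials per setting:

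| r | Either test significant | Tests disagree |
|---|---|---|
| 0.12 | 5.9% to 6.0% | 1.8% |
| 0.25 | 6.3% | 2.6% |
| 0.37 | 6.7% | 3.5% |

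Shorter runs give 5.9% to 6.1% for r 0.12 to 0.25. None of these figures includes covariate selection.

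**Disagreement at the planned effect.** With a true difference of 1.75D and SD held at 1.50D (1,000,000 trials), the tests disagree on significance in 4.7% of trials at r = 0.12 and 6.3% at r = 0.25.

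**Chance imbalance.** The standard error of the baseline difference is baseline SD × √(2/13), or 0.196D to 0.226D. Two standard errors are 0.39D to 0.45D. Times the slope, the shift in the t-test estimate runs from 0.392 × 0.369 = 0.145D to 0.453 × 0.508 = 0.230D, which is 8% to 13% of 1.75D.

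**Power.** For ANCOVA the residual variance is multiplied by (1 − r²)(1 + 1/(2n − 4)), with 2n − 3 degrees of freedom. At n = 13 the second factor is 1 + 1/22 = 1.045.

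| SD of change | t-test | ANCOVA, r implied above |
|---|---|---|
| 1.50D | 81.4% | 80.1% to 80.3% |
| 1.36D | 88.2% | 87.5% to 87.8% |
| 1.17D | 95.5% | 95.5% to 95.8% |

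Break-even is near r = 0.2. At SD 1.50D, ANCOVA reaches 86.0% at r = 0.4 and 89.5% at r = 0.5.

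**The case against.** The strongest reply is that *basic* followed by covariate adjustment is ordinary wording for a main analysis and a supporting one. A randomised t-test is unbiased, holds its 5% error, and has a standard error that already allows for chance imbalance. The excess error from the pair is about one point, and the imbalance example is a 2-standard-error event. All of this is right as arithmetic, and it keeps the point modest. It does not supply the missing rule: the text never says that *basic* means deciding, and on that reading the ANCOVA still carries an open covariate list at the same 0.05.

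A reader might also infer that the plan gives up precision or power by putting the t-test first. The documents do not support that. The baseline ANCOVA is already planned, and at the stated SDs of change it gains essentially nothing. A larger gain appears only if the 0.90D in section II is used, but that is the spread of refraction at 18 months among infants generally, not of change in high hyperopes.

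Nor does section II show that baseline predicts change. It reports the chance of reaching a fixed endpoint, which falls with higher baseline even when change is unrelated to baseline. The slope used above also implies untreated decreases of 3.00D or more, against the 1.2D to 1.34D in the sample size paragraph. It serves only to set a scale.

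**Conclusion.** The defect stands in limited form: one contrast, two tests at 0.05, a second model left open to data-driven covariates, and no rule on which decides. The size is small but real: about 6% error instead of 5% at one age, and disagreement in about 5% to 6% of trials at the planned effect. An unlucky allocation would leave roughly 0.15D to 0.23D in the t-test estimate. These figures assume 13 completers per arm, one value per infant, normal changes, and r of 0.12 to 0.25, which is a rough inference. The effect of choosing covariates by imbalance testing is not quantified and would come on top.

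The second age is a separate and larger source of multiplicity. With an assumed 0.7 correlation between the two changes and r = 0.14, the t-test alone at both ages gives 8.5%, and both tests at both ages give 10.0%. Naming the deciding test does not settle that. No claim of improved power should be attached to this point; it would need r near 0.4 or more.

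**What to change.** In section F, state that the deciding analysis of change in refractive error is an ANCOVA with treatment arm and 3-month refractive error as the only terms, with both eyes handled by the within-infant method that the section already requires. Remove covariate selection by imbalance testing from that analysis. Report the unadjusted t-test and any further-adjusted models as supportive, with no claim attached. Make the same choice for relative peripheral refraction, with 3-month peripheral refraction as the covariate.

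The cost is a short edit, one degree of freedom, and up to about 1 point of power if baseline is only weakly related to change. No new data are needed. The deciding age still has to be named separately before there is a single primary result.
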